10.4.3 Categorization of Outcomes

The outcome may be classified as: recovered/resolved (e.g., without sequelae); recovered/resolved with sequelae; not recovered/not resolved; fatal; or unknown (if follow-up is not possible).

If the outcome of an AEFI is reported as recovered/resolved with sequelae, the investigator must specify the type of sequelae on the AEFI form. If the outcome of an AEFI is reported as unknown, the investigator must specify (on the AEFI form) the rationale for selecting “unknown.”

"Fatal" must be recorded as an outcome when the AE results in death. The cause of death is required when known. If an autopsy was performed, an autopsy report must be provided. If an autopsy was not performed, a death certificate must be provided, if obtainable. Death will be reported as an outcome and not as an event. If more than one AEs is possibly related to the participant's death, the outcome of death should be attributed to the AE that, in the investigator's opinion, is the most plausible cause of death. All other ongoing AEs/AEGs should be recorded as unrecovered/unresolved at the time of death.

10.5 Recording and Reporting

10.5.1 Persistent or recurrent adverse events

AEs that persist continuously, without resolution, between clinical trial assessments should be recorded. A new event should be documented whenever the severity of an event changes. AEs that resolve and then recur should have each recurrence recorded separately in the medical record.

10.5.2 Diagnosis versus signs and symptoms

Whenever possible, the investigator should report a diagnosis rather than individual signs and symptoms or abnormal laboratory values. However, if a cluster of signs and/or symptoms cannot be clinically characterized as a single diagnosis or syndrome at the time of reporting, each individual event should be recorded in the medical record. If a diagnosis is established later, all previously reported AEs based on signs and symptoms should be canceled and replaced with an AE report based on that single diagnosis, with an onset date corresponding to the onset date of the first symptom of the eventual diagnosis.

The investigator should use standard medical terminology/concepts and avoid colloquial terms and abbreviations. Only one AD term should be recorded in each event field in the medical record.

10.5.3 Pre-existing clinical conditions

A pre-existing condition is one that is present at the screening visit for this study. This condition must be recorded on the medical history form. A pre-existing condition should only be recorded as an AE if the frequency, severity, or nature worsens during the study. When recording these events in the AE clinical record, it is important to indicate the concept of change regarding the pre-existing condition, including applicable descriptors (e.g., “more frequent headaches”)

10.5.4 Clinical Laboratory Tests

Not every laboratory test with results outside the reference range qualifies as an AE. A laboratory test result should be reported as an AE if it meets any of the following criteria:

- Be accompanied by clinical symptoms
- Result in a change in the study treatment (e.g., modification of the dosage regimen, discontinuation of treatment, or discontinuation of the study)
- Result in an unplanned medical intervention
- Show a change in a parameter from a normal value to a pathological value or a further worsening of an already pathological value
- be considered clinically significant in the investigator’s opinion

It is the investigator’s responsibility to review all laboratory results. Medical and scientific judgment must be exercised to decide whether an isolated laboratory abnormality should be classified as an ADE. When evaluating such changes, the extent of the deviation from the reference range, the duration until return to the reference range—whether during continuous treatment or after discontinuation of treatment with the investigational product—and the range of variation of the respective parameter within its range must be taken into account.

The researcher is responsible for determining the clinical significance of each abnormality.

If pathological laboratory values are present at the end of the treatment phase that were not present at baseline, additional clinical or laboratory investigations must be conducted until the values return to the reference range or a plausible explanation (e.g., concomitant disease) for the pathological laboratory values is found. The investigator must decide, based on the above criteria and the participant’s clinical condition, whether a change in a laboratory parameter is clinically

significant and therefore constitutes an ADE. If the investigator considers this ADE to be serious, it must be reported as a SAE.

If a laboratory abnormality meeting the above criteria is a sign of a disease or syndrome, only the diagnosis should be recorded in the medical record. If a laboratory abnormality that meets the above criteria is not a sign of a disease or syndrome, the abnormality itself should be recorded in the medical record, along with a descriptor indicating whether the test result is above or below the normal range (e.g., “elevated potassium” rather than “abnormal potassium”). If the laboratory abnormality can be characterized by a precise clinical term according to standard definitions, the clinical term should be recorded as the AE, for example, hypercalcemia or hypoglycemia. The initial severity of the event should be recorded, and the severity should be updated at any time if the event worsens.

All pathological laboratory values/findings diagnosed during the treatment period must be reviewed by the investigator to provide a final clinical assessment in light of the dynamics of the laboratory changes/abnormalities.

10.5.5 Abnormal vital signs and other abnormalities

Laboratory results, ECGs, vital signs, and other non-standard safety assessments will be considered AEs if they meet at least one of the following criteria:

- They are associated with symptoms or result in a diagnosis (in which case, the symptom or diagnosis will be recorded as an ADR)
- Lead to discontinuation of the investigational product
- Require treatment or referral of the participant for additional off-protocol testing (retesting or titration are within the protocol procedures).

It is the investigator’s responsibility to review all vital signs, ECGs, and other safety findings. Medical and scientific judgment should be exercised to decide whether an isolated laboratory abnormality should be classified as an AE. If a clinically significant abnormality is a sign of a disease or syndrome (e.g., high blood pressure), only the diagnosis (e.g., hypertension) should be recorded in the medical record.

Observations regarding the same clinically significant laboratory abnormality between visits should not be recorded repeatedly, unless there are changes in the etiology. The initial severity of the event should be recorded, and the severity should be updated at any time if the event worsens.

10.6 Adverse drug reactions and reference safety information

10.6.1 Adverse drug reaction

An adverse drug reaction (ADR) is an undesirable and unintended response to a drug related to any administered dose. This definition implies a reasonable possibility of a causal relationship between the event and the investigational drug. This means that there are facts (evidence) or arguments suggesting a causal relationship.

Given that the investigational drugs have been commercially approved by ANVISA for decades, in this study only adverse reactions not yet described in ANVISA's drug dossier and assessed by the investigator as having a reasonable causal relationship with a drug (under investigation) will be considered ADRs. Thus, no reports of ADRs related to the drugs used in this study are expected.

10.6.2 Safety Reference Information

Basic safety information (RSI) forms the basis for assessing the predictability of an AEF for accelerated reports and annual safety reports, as well as for the safety monitoring of clinical trial participants by regulatory agencies (or ethics committees). In the context of this study, no ADR reports are expected, as potential adverse reactions are expected to already be described in the SIR for the investigational drugs (, and ANVISA Drug Dossier, and the package insert for the drug registered with ANVISA), except in exceptional cases, for the investigational medical products in this study.

10.7 Serious adverse event

10.7.1 Definition of a serious adverse event ()

A SAE is defined as any adverse medical event that, at any dose:

Results in death

Be life-threatening (the term “life-threatening” in the definition of severity refers to an event during which the participant was at risk of death; it does not refer to an event that hypothetically could have caused death if it had been more severe)

Require hospital admission or prolongation of an existing hospitalization. Hospitalizations for elective surgery (i.e., a planned, non-emergency medical procedure), social hospitalizations, and hospitalizations lasting less than 24 hours are not considered SAEs

Result in persistent or significant disability/impairment

Be a congenital anomaly/birth defect

Be a significant medical event (i.e., clinically significant)

Medical and scientific judgment must be exercised to decide whether prompt reporting is appropriate in other situations, such as for medically significant events that may not be an immediate life-threatening event or result in death or hospitalization, but that may put the participant at risk or require intervention to prevent one of the other outcomes listed in the definition above. These events should also be considered serious.

Any worsening of a pre-existing condition or any new condition that meets the above SAE criteria should be considered an SAE, and the investigator is encouraged to discuss with the study coordination any SAE for which the severity assessment is uncertain or questionable.

The following situations are not considered SAEs:

Elective or pre-planned surgery for a pre-existing condition that has not worsened

Routine health evaluations requiring hospitalization not associated with a deteriorating clinical condition

Social hospitalization (homelessness, family circumstances, etc.)

Adverse reactions associated with the investigational drugs, which are expected for such drugs according to the drug dossier registered with ANVISA

Results under investigation

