	
 12. Pregnant women or women of childbearing age who do not agree to use an effective method of contraception for 90 days from the date of signing this consent form; 13. Women who are breastfeeding; 14. Expected hospitalization for elective surgical procedures lasting more than 48 hours; 15. Contraindications for the METFORMIN arm 
 a. Participants currently taking metformin; b. Participants with creatinine clearance < 30 ml/min, a history of KIDIGO IV, or currently undergoing dialysis. 16. Contraindications for the FLUVOXAMINE arm 
 a. Use of serotonin reuptake inhibitors (donepezil, fluoxetine, escitalopram, paroxetine); 17. Current severe comorbid psychiatric disorder (e.g., clinical depression, anxiety, sleep disorder, eating disorder, substance abuse) that is uncontrolled and associated with significant symptoms or requiring the use of a medication contraindicated in this study; 18. Clinical history of moderate to severe hepatic impairment or hepatic cirrhosis with a Child-Pugh score of C or higher; 19. Clinical history of severe chronic lung disease with significant limitation of activities; 20. Inability of the participant to provide informed consent or adhere to the procedures proposed in the study; 21. Taking medications known to cause chronic fatigue as a side effect (except for participants with chronic cardiovascular disease who are on chronic beta-blocker therapy); 22. Known hypersensitivity and/or intolerance to fluvoxamine or metformin; 23. Any clinical condition that, in the investigator's opinion, may preclude participation in this study.
Primary and secondary outcomes:	
The primary outcome is a reduction in the FSS score of at least one standard deviation 60 days after randomization.
 
The secondary outcomes are:
 
 1. The FFS score 30 days after randomization. 2. The FFS score 90 days after randomization. 3. HRQL, assessed using the EuroQol-5D-5L 60 days after randomization. 4. All-cause mortality up to 60 days after randomization. 5. Unexpected hospitalization from any cause up to 60 days after randomization. 6. Safety and tolerability of the investigational products 7. Adverse events experienced by participants during treatment
Procedures	Screening procedures

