10 EVALUATION, RECORDING, AND REPORTING OF ADVERSE EVENTS

10.1 *Definition of Adverse Events*

²²⁸An adverse event is any unfavorable medical occurrence experienced by a patient or clinical trial participant who has received a drug and that does not necessarily have a causal relationship with that treatment. Therefore, an ADE may be any unfavorable and unintended sign (including an abnormal laboratory finding), symptom, or illness temporarily related to the use of an (experimental) drug, whether or not it is related to the (experimental) drug. This includes:

- (1) Any new clinical condition, sign, or symptom, clinically significant physical examination abnormality, or newly diagnosed event occurring during the ADR reporting period, including signs or symptoms associated with an underlying condition that was not present prior to the ADR reporting period;
- (2) A preexisting condition that has worsened in severity or frequency or changed in character after the participant signed the RCT during the ADR reporting period; and
- (3) Complications that occur as a result of interventions required by the protocol. An ADE may arise from any use of the investigational drug (e.g., off-label use, use in combination with another drug) and from any route of administration, formulation, or dose, including an overdose. Any side effects, harm, toxicity, or hypersensitivity reactions that may occur in a participant in this clinical trial may also be considered AEs.

For the purposes of this protocol, events that will not be considered AEs include:

- Fluctuating signs or symptoms expected from a pre-existing medical condition (e.g., tremor in a participant with Parkinson's disease; migraine episodes) that did not worsen in severity or frequency or change in character during the ADE reporting period;
- Surgeries or medical procedures are not AEs; however, the clinical condition (new or worsened) that led to the surgery or medical procedure is the reported AE (e.g., for appendicitis resulting in an appendectomy, the appendicitis should be reported as the AE);
- Overdose without clinical signs or symptoms.

10.2 *Adverse Event Reporting Period*

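### Section 10.7.1 states two elective-surgery exemptions from SAE status that do not agree, so a planned admission for a new or worsened condition can be classified either way

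*Protocol*

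**What the plan says.** Protocol section 10.7.1 defines an SAE through a set of seriousness criteria, one of which is hospital admission or prolonged hospitalisation. That criterion has its own exemption: "Hospitalizations for elective surgery (i.e., a planned, non-emergency medical procedure), social hospitalizations, and hospitalizations lasting less than 24 hours are not considered SAEs". Elective surgery is glossed there as any planned, non-emergency procedure, and nothing is said about why the procedure is needed.

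The same section closes with a list of situations that are not SAEs. On surgery it says: "Elective or pre-planned surgery for a pre-existing condition that has not worsened". On other admissions it says: "Routine health evaluations requiring hospitalization not associated with a deteriorating clinical condition". Between the two stands a rule on new or worsened disease: "Any worsening of a pre-existing condition or any new condition that meets the above SAE criteria should be considered an SAE".

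Two other places bear on the point. Section 10.1 says that a procedure is not itself an AE, but that "the clinical condition (new or worsened) that led to the surgery or medical procedure is the reported AE". Section 10.7.2 requires every SAE, related or not, to be reported within 24 hours.

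**The concern.** Both sentences govern the same decision, whether an admission for planned surgery is serious, and they draw the line in different places. One looks only at whether the procedure was planned. The other also asks whether the condition existed before and is unchanged.

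The admissions on which they differ are the ones that matter for safety: a participant develops a condition, or an existing one worsens, during treatment, and it is then dealt with by a scheduled operation. If sites read the section differently, the same event is an SAE at one centre and a non-serious AE at another. Only the first goes into the 24-hour report and the SAE count. Safety of both drugs is a stated secondary objective, so the count is meant to be used.

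**Working it through.** No sample size, power or error rate is involved, and the protocol gives no figure to reproduce. The check is to take each type of admission and apply the two statements in section 10.7.1 in turn.

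| Type of admission | Exemption in the hospitalisation criterion | Closing list of non-SAEs | Result |
|---|---|---|---|
| Planned surgery, pre-existing condition, not worsened | Exempt | Exempt | Agree |
| Planned surgery, new or worsened condition | Exempt | Not exempt | Disagree |
| Social admission | Exempt | Exempt | Agree |
| Unplanned stay under 24 hours | Exempt | Not mentioned | No contradiction |

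Only the second row is in conflict. Three further steps show whether the rest of the protocol settles it.

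1. The rule on new or worsened disease does not. It applies to a condition that meets the criteria stated above it, and one of those criteria is the hospitalisation criterion with its unconditional exemption. The reader is sent back to the sentence in dispute.
2. Section 10.1 does not settle it either, though it shows the direction of the protocol's thinking. The new or worsened condition behind a procedure must be recorded as an AE, so the event enters the database. Whether it is serious is a separate step, and that is where the two statements part.
3. The other seriousness criteria can settle individual cases. Section 10.7.1 keeps death, threat to life, disability, congenital anomaly and the medically significant event, and none of these depends on how an admission was planned. An event that meets one of them is an SAE under either reading. The conflict remains for events whose only claim to seriousness is the admission.

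**The case against.** The strongest reply is that the two statements can be combined. Both say what is not an SAE; falling outside the list does not by itself make an event serious. If both exemptions apply, the broader one governs, and the section can be read together with section 10.1: the planned admission is not the event, and the underlying condition is judged on its own seriousness. This is a possible reading, and the logical point stands. But under it the list's restriction to pre-existing, unworsened conditions has no effect on the hospitalisation criterion. A site that gives the restriction meaning will reach the other answer. The text does not say which is intended.

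The reply is also right that the reach is limited. The medically significant route is open, and the section invites investigators to discuss doubtful cases with study coordination. Expected elective admissions of more than 48 hours are excluded at entry (section 5.3, item 14), and surgery scheduled within 60 days is recorded at baseline (section 8.2).

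Three stronger conclusions might be inferred, and the documents do not support them.

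- That serious new conditions go uncounted. They remain AEs under section 10.1 and may be SAEs by another criterion. What is at risk is consistent classification.
- That the planned-procedure exemption clashes with the hospitalisation outcome. The outcome in the Protocol Overview is "Unexpected hospitalization from any cause up to 60 days after randomization", and section 8.3 speaks of unplanned admissions, so planned procedures generally lie outside it.
- That the exemption for stays under 24 hours is an error and should go. No other sentence contradicts it; it is a choice of definition. The hospitalisation outcome has no minimum stay, so a short emergency admission can be an outcome event without being serious on this criterion. Removing the rule would still not make the two counts agree. The closing list also exempts expected drug reactions and "Results under investigation", which appears to mean the study outcomes. The SAE window also runs to the day 90 visit (section 10.7.2), against day 60 for the outcome.

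**Conclusion.** The point holds for one class of event: a planned admission for a condition that is new or has worsened on study treatment and that meets no other seriousness criterion. For this class section 10.7.1 supports both answers, which makes SAE counts by arm and 24-hour reporting inconsistent between sites.

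The size cannot be put in numbers. The protocol states no rate of admission or of planned surgery, and any event count would rest wholly on assumed rates. Given the entry exclusion and the other routes to seriousness, the matter is minor. The study is double-blind and randomisation is stratified by facility (section 12.2), so there is no reason to expect the differing readings to favour one arm systematically. The harm is to completeness and comparability of the SAE data. The conclusion rests on the wording alone and assumes that no separate instruction to sites already resolves it.

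**What to change.** Reconcile the two statements in section 10.7.1. Make the elective-surgery exemption in the hospitalisation criterion subject to the condition in the protocol's own list, so that it covers only surgery for a condition present before the study and not worsened since. A cross-reference from the criterion to the list would do the same with less text. The exemptions for social stays and for stays under 24 hours need no change on this account.

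It would help to add one sentence saying that SAE counts and the unplanned-hospitalisation outcome are defined differently and are not expected to match.

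The cost is one change of wording, carried through the amendment process of section 16.2, and a note to sites. Section 3.3.2 refers to the first 100 recruited participants, so recruitment has begun; planned admissions already on file should be checked once against the reconciled text. No treatment, visit or analysis is affected.

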10.4.2 Causality and Reporting

The investigator will provide a causality assessment for all AEs using their best clinical judgment based on the available medical information regarding the event being reported. The causality assessment will be reevaluated as new information becomes available. If the investigator's causality assessment is not reported, the event will be considered "related" until such information is received. Each investigator will assess the degree to which the ADR is related to the investigational drugs using the following definitions:

Unrelated: There is no reasonable possibility that the investigational product caused or contributed to the ADE.

- The event is related to an etiology other than the investigational drug, such as an underlying disease, study-unrelated procedures, concomitant medication, or the subject's clinical condition.
- The timing of the ADE is not reasonably related to the administration of the investigational drug.

Related: There is a reasonable possibility that the investigational product caused or contributed to the AE.

- There is no compatible temporal association between the event and the administration of the investigational drug.
- Is there a biologically plausible mechanism by which the study treatment could have caused or contributed to the ADE?
- The event improves or resolves after discontinuation of the study drug without the initiation of any specific treatment for the event (withdrawal from exposure) and/or the event recurs or worsens after reintroduction of the study therapy.
- The event cannot reasonably be attributed to a concomitant or underlying disease or to other medications or procedures.

For the purposes of causality assessment, "reasonable possibility" means that, based on the investigator's medical judgment regarding the available information, there are facts or arguments suggesting a positive causal relationship.

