10.7.2 Reporting of serious adverse events

The SAE reporting period begins when the consent form is signed by the participant. The SAE reporting period ends at the 90-day visit.

The occurrence of an SAE must be reported immediately to the study monitoring committee within 24 hours of its notification via fax, email, or telephone. This includes all SAEs (regardless of their relationship to the study treatment).

A death occurring during the study or reported to the investigator, whether considered treatment-related or not, must be reported to the study monitoring committee.

Any SAE considered to have a causal relationship (e.g., related) with the investigational product and discovered by the investigator at any time after the study must be reported. The investigator must provide a rationale for the assessment of a causal relationship. All safety information obtained after the clinical database has been closed must be documented in the safety database, and the implications for handling the data in the clinical database must be evaluated on a case-by-case basis.

The onset date of an SAE is defined as the date on which the signs/symptoms/diagnoses became serious (i.e., meet at least one of the severity criteria). If a participant experiences an AE and it progresses to an SAE, a new SAE must be recorded. The resolution date of the original AE must be the same as the onset date of the SAE. However, when the AE is resolved and the pre-existing AE is still ongoing, this should be recorded as a new AE. The resolution date of an AE is defined as the time when symptoms disappear or when the event is considered chronic (e.g., sequelae) or stable and/or if the severity criteria are no longer applicable.

The investigator must complete the EAS report form and verify the accuracy of the information recorded on the EAS pages against the source documents. The sponsor's EAS report form must be completed in capital letters, using medical terminology, in English, and within the specified time limits. Any supporting documentation (e.g., hospital discharge summary, autopsy report/death certificate, etc.) must be submitted/transmitted with the SAE report form (attachment). The supporting information provided must not reveal the participant's identity beyond the agreed-upon study identifier. The investigator must ensure that the reported information is accurate and consistent.

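### Section 10.7.1 takes dossier-listed drug reactions out of the SAE category whatever their outcome, so serious known reactions would be missing from SAE and ADR counts and from 24-hour reporting

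*Protocol*

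**What the plan says.** Section 10.7.1 opens with a rule based on outcome: "A SAE is defined as any adverse medical event that, at any dose" meets one of the listed criteria. Expectedness is not a condition. Further down, under "The following situations are not considered SAEs", the section lists "Adverse reactions associated with the investigational drugs, which are expected for such drugs according to the drug dossier registered with ANVISA". The last item in that list is a short, unexplained entry on results under investigation.

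Section 10.6.1 narrows the adverse drug reaction in the same way: "in this study only adverse reactions not yet described in ANVISA's drug dossier and assessed by the investigator" as causally related are to count. It concludes: "Thus, no reports of ADRs related to the drugs used in this study are expected". Section 10.6.2 repeats that no ADR reports are expected.

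Section 10.7.2 requires SAEs to be reported within 24 hours and says "This includes all SAEs (regardless of their relationship to the study treatment"). It also requires every death to be reported. Section 10.7.3 defines a SUSAR as an ADR that is both serious and unexpected.

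In Section 10.4.2, the first of four bullets under 'Related' reads: "There is no compatible temporal association between the event and the administration of the investigational drug".

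**The concern.** Seriousness describes what happened to the participant. Expectedness describes whether the reaction was already known. Sections 10.7.1 and 10.6.1 use the second to switch off the first.

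Safety of both drugs is a stated objective (Section 2.2), and the DMC's stated role is to monitor participant safety (Section 11.1). Section 10.6.2 itself anticipates that potential reactions are already described in the reference safety information. On the protocol's own account, then, the exclusion covers nearly all serious harm that the drugs might cause. Sites apply these definitions when an event is first reported, so a later analysis plan cannot recover a seriousness flag that was never set.

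**Working it through.** The protocol states no figure on this point, so the main check is to set the sections side by side.

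**1. Is the exclusion limited by seriousness?** No. Take a listed reaction that leads to hospital admission or threatens life. It meets the criteria at the top of Section 10.7.1 and is removed by the list at the bottom, so the section contradicts itself. Section 10.4.1 (an SAE is an AE meeting any of the regulatory criteria) and Section 10.5.4 (a laboratory event judged serious must be reported as an SAE) both side with the general rule.

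**2. Does another category catch the event?** It is not an ADR, because Section 10.6.1 admits only undescribed reactions. It is not a SUSAR, because Section 10.7.3 requires an ADR. The 24-hour rule in Section 10.7.2 applies to SAEs, so it does not cover the event either. The word 'unexpected' in the SUSAR definition already does the job that the two exclusions attempt.

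**3. What still records it?**
- All AEs are collected from consent to the end-of-study visit (Section 10.2), and side effects and toxicity may be AEs (Section 10.1).
- The safety row of the Section 12.11 table is a descriptive analysis of adverse events by group, not restricted to SAEs or ADRs.
- Every death is reported (Section 10.7.2).
- All-cause mortality and unexpected hospitalization to day 60 are secondary outcomes.

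**4. What do those records miss?** AEs are graded by intensity, which Section 10.4.1 itself separates from seriousness, so an AE table would not show which listed reactions were serious. Life-threatening, disabling or medically significant listed reactions have no separate capture. Hospitalization is analysed to day 60, while SAE reporting runs to the 90-day visit. One hospitalization row in Section 12.11 also names deaths as its measure.

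**5. Direction of bias.** Let r be the true excess rate of serious listed reactions on active drug, b the background rate of the same event types in every arm, and f the fraction of such events that blinded investigators attribute to the drug and call expected. The recorded rates of these events are (b + r)(1 − f) on active drug and b(1 − f) on placebo. The recorded difference is r(1 − f), which is never larger than the true difference r and falls to 0 as f approaches 1. This takes f to be the same in each arm, as blinding (Section 6.1) would suggest.

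**6. Size, on assumed inputs.** Neither r nor f is in the protocol. Cases losing SAE status in an arm of 500 because of the drug = 500 × r × f. With r = 1%:
- f = 0: 500 × 0.01 × 0 = 0 cases
- f = 0.5: 500 × 0.01 × 0.5 = 2.5 cases
- f = 1: 500 × 0.01 × 1 = 5 cases

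The count scales in proportion to r. If the recorded count were 0 of 500, the upper limit would be 1 − 0.05^(1/500) = 0.60% (one-sided 95%) or 1 − 0.025^(1/500) = 0.74% (two-sided 95%). In the extreme case f = 1, either limit would lie below the assumed true rate of 1%, and the zero would come from the definition.

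**7. The 'Related' bullet.** The lead sentence is affirmative: "Related: There is a reasonable possibility that the investigational product caused or contributed to the AE". Only the first of the four bullets is negated. It points the same way as the timing bullet under 'Unrelated', so timing no longer separates the two categories.

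**The case against.** The strongest reply is that little is lost. All AEs are collected and described by arm, every death is reported, hospital admissions to day 60 are counted and adjudicated blind to treatment (Section 11.2), and Section 7.2 describes mainly mild or self-limiting reactions. No efficacy analysis, sample size or decision rule in the document uses SAE or ADR counts. Most of this stands, and it limits the point to lost SAE and ADR status and lost 24-hour reporting. It does not remove the point, because the AE record carries intensity and not seriousness.

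Several stronger readings are tempting and are not supported:
- A reader might infer that serious known harms are left out of the safety results altogether. Sections 10.2, 10.7.2 and 12.11 show otherwise.
- A reader might infer that the causality test is reversed. One bullet of four is negated, possibly a translation slip. It removes no event, since SAE reporting does not depend on relatedness and a missing causality assessment defaults to 'related'.
- A reader might infer that Section 10.7.2 is directly contradicted. That section governs events already classed as SAEs; the contradiction lies within Section 10.7.1.
- A reader might take the entry on results under investigation to exclude deaths and hospitalizations from SAEs. It may mean study outcomes, but the protocol does not say so. It needs clarifying before anyone decides to delete it.

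The five-case figure is also a worst case: it needs a blinded investigator to attribute every case to the drug and judge it expected.

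**Conclusion.** The concern holds in limited form. As written, Sections 10.7.1 and 10.6.1 take serious dossier-listed reactions out of the SAE count, the ADR count and 24-hour reporting, leaving them as ordinary AEs graded by intensity. Deaths, and hospitalizations to day 60, are still captured separately. The SAE comparison with placebo would be biased toward no difference, by the factor (1 − f) on the excess of these events. This assumes that attribution is equally likely in each arm.

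The size cannot be fixed from the protocol: 0 to 5 cases per arm of 500 at an assumed 1% rate, depending on attribution. The finding itself rests on the wording and needs no assumed rate. The negated bullet in Section 10.4.2 is a separate minor error that makes causality coding unreliable.

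**What to change.** - In Section 10.7.1, delete the expected-reactions bullet and classify seriousness by the outcome criteria only.
- In Section 10.6.1, define an ADR as any AE with a reasonable causal relationship to the drug, and bring Section 10.6.2 into line.
- Use expectedness only to identify SUSARs and expedited reports.
- State that all SAEs are tabulated by arm.
- Say what the entry on results under investigation means, and reconcile it with the rule in Section 10.7.2 that all deaths are reported.
- As a separate minor correction, make the first 'Related' bullet in Section 10.4.2 say that a compatible temporal association exists.
- Review events already classed as non-serious under the present rule and reclassify where needed.

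The cost is a protocol amendment, revised SAE form instructions and the look-back. The lasting downside is more SAE reports to process.
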